### **4.2. Clinical Study Summary**

#### **4.2.1. Pathway PVD clinical study**

The Pathway PVD clinical study was a prospective, multicenter, single arm study conducted using the Pathway PV System, a first-generation model of Jetstream, in which a total of 172 subjects were enrolled at 9 investigational sites in Germany, Austria, and Belgium.

The primary safety endpoint was the freedom from major adverse events (MAE) including clinically driven target lesion revascularization (TLR), any death, target vessel revascularization (TVR), myocardial infarction (MI), and index limb amputation at 30 days post procedure. The primary effectiveness endpoint was a reduction in mean percent stenosis, with and without adjunctive therapy.

The secondary endpoints included: (1) MAE at 6 months, (2) absence of death or amputation as a result of the Pathway PV System during the follow-up period, (3) clinical success defined as  $\geq 1$  clinical category improvement of Rutherford scale (or equivalent) from baseline at 6 and 12 months; (4) hemodynamic success defined as a  $> 0.1$  improvement in the ABI during the period from baseline to 30 days post procedure and no deterioration  $> 0.15$  from the maximum early post procedure level at 6 and 12 months. Target lesions had reference vessel diameters ranging from 3 – 5 mm (visual estimation), total lesion lengths (alone or series of lesions) up to 10 cm for the femoropopliteal arteries as well as up to 3 cm for the tibial or peroneal arteries (Rutherford categories 1–5 or equivalent).

The 30-day freedom from MAE was 99% (170/172), with 2 amputations planned prior to the intervention being performed (Table 4.2-1). No procedure or device related amputations occurred.

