### 6.2.2. Additional Endpoints

- Procedural success, defined as  $\leq 30\%$  residual angiographic stenosis in 2 near-orthogonal projections by visual assessment, after successfully debulking the target lesion and adjunctive interventions (such as percutaneous transluminal angioplasty/stenting) without any MAE within 24 hours post index procedure
- Primary vessel patency of the treated segment assessed by duplex ultrasound sonography (DUS) at 6 and 12 months post-procedure without TLR\*
- Clinical success rate (defined as improved Rutherford classification by at least +1 class compared to baseline) at 30 days, 6 and 12 months
- Hemodynamic success rate (defined as positive change in Ankle-Brachial Index) at 30 days, 6 and 12 months
- MAE rate 6 and 12 months post-index procedure
- All-cause death at 30 days, 6 and 12 months
- Clinically-driven TLR and TVR rate at 30 days, 6 and 12 months
- Target limb major amputation at 30 days, 6 and 12 months
- Rate of peri-procedural complications:
  - Perforation at treated segment
  - Abrupt closure at treated segment (including dissection and thrombosis)
  - Significant dissection (types C – F) at treated segment
  - Aneurysm at treated segment
  - Distal embolization

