### **7.2.1. *Treatment and Control***

Subjects enrolled in this clinical trial will not be randomized, and there is no control group in this study. All eligible subjects will receive treatment with the Jetstream System.

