**25.2. Definitions**

**Table 25.2-1: Definitions**

Term	Definition
AMPUTATION	
 
Major Amputation: amputation of the lower limb at the ankle level or above; and can be further specified as below-the-knee and above-the-knee amputations, as well as planned and unplanned amputations.
 
Minor Amputation: amputation of the lower limb below the ankle level, i.e. forefoot or toes.
 

ANKLE-BRACHIAL INDEX (ABI)	
The ratio between the systolic pressure measured at the ankle and the systolic pressure measured in the arm as follows:
 
 
Ankle: The systolic pressure will be measured in the target limb at the arteria dorsalis pedis and/or the arteria tibialis posterior. If both pressures are measured, the highest pressures will be used for the ABI calculation.
 
Brachial: The systolic pressure will be measured in both arms, and the highest of both pressures will be used for the ABI calculation.
 
 
An ABI <0.9 indicates the presence of peripheral arterial disease in symptomatic patients as well as in asymptomatic patients. In addition, an ABI <0.9 reflects the presence of generalized asymptomatic or symptomatic atherosclerotic disease, and its associated increased cardiovascular risk.

ARRHYTHMIA	Any variation from the normal rhythm of the heartbeat, including but not limited to, sinus arrhythmia, premature beats, heart block, ventricular or atrial fibrillation, ventricular tachycardia, or atrial flutter.
ASSISTED PRIMARY PATENCY	Percentage (%) of lesions without clinically-driven TLR and those with clinically-driven TLR (not due to complete occlusion or by-pass) that reach endpoint without restenosis.
BLEEDING COMPLICATION	Includes, but is not limited to, intracranial hemorrhage, GI bleeding, hematoma, bleeding at percutaneous catheterization site, and/or retroperitoneal bleeding. Bleeding that requires surgery qualifies as an SAE.
CALCIFICATION	Readily apparent densities seen within the artery wall and site of lesion as an x-ray-absorbing mass.

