**Table 25.2-1: Definitions**

Term	Definition
DIAMETER STENOSIS	The maximal narrowing of the target lesion relative to the reference vessel diameter.
DISSECTION- NHLBI GRADE TYPES	Type A- Small radiolucent area within the lumen of the vessel disappearing with the passage of the contrast material. Type B- Appearance of contrast medium parallel to the lumen of the vessel disappearing within a few cardiac cycles. Type C- Dissection protruding outside the lumen of the vessel persisting after passage of the contrast material. Type D- Spiral shaped filling defect with or without delayed run-off of the contrast material in the antegrade flow. Type E- Persistent luminal filling defect with delayed run-off of the contrast material in the distal lumen. Type F- Filling defect accompanied by total vessel occlusion.
DISTAL EMBOLIZATION	Migration of a filling defect, or thrombus, to distally occlude the target vessel or one of its branches.
HEMATOMA	A localized swelling filled with blood resulting from a break in a blood vessel.
HEMODYNAMIC IMPROVEMENT	Improvement of ABI by $\geq 0.1$ or to an ABI $\geq 0.90$ as compared to the pre-procedure value without the need for repeat revascularization.
HEMODYNAMIC SUCCESS	Hemodynamic success is defined as a positive change in Ankle-Brachial Index compared to baseline.
HYPOTENSION	Systolic blood pressure $< 80$ mmHg lasting more than 30 minutes or requiring intervention (e.g. pacing, IABP, intra venous vasopressors to sustain systolic blood pressure). This excludes transient hypotension or vagal reactions, which are self-limited or readily reversible.
INTIMAL FLAP	An extension of the vessel wall into the arterial lumen.
LESION LENGTH	Measured as the distance from the proximal shoulder to the distal shoulder of the lesion, in the view that demonstrates the stenosis in its most elongated projection.
MAJOR ADVERSE EVENTS (MAEs)	Major Adverse Events (MAEs) include all-cause death, target limb unplanned major amputation and/or target lesion revascularization (TLR).

Table 25.2-1: Definitions

Term	Definition
MINIMAL LUMEN DIAMETER	The vessel diameter as measured at the narrowest point of the lesion.

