5 ADDITIONAL STATISTICAL ANALYSES

5.1 Secondary Endpoints Assessments

Secondary assessments may refer to (but not limited to) peri-procedural complications, clinical/procedural/hemodynamic success, safety/effectiveness endpoints, any type of AE rates at time points that data is collected (refer to the protocol section 7.2). All additional assessments are observational

- Procedural success, defined as $\leq 30\%$ residual angiographic stenosis in 2 near-orthogonal projections by visual assessment, after successfully debulking the target lesion and adjunctive interventions (such as percutaneous transluminal angioplasty/stenting) without any MAE within 24 hours post index procedure
- Primary (vessel) patency of the treated segment assessed by duplex ultrasound sonography (DUS) at 6 and 12 months post-procedure without TLR
- Clinical success rate (defined as improved Rutherford classification by at least +1 class compared to baseline) at 30 days, 6 and 12 months
- Hemodynamic success rate (defined as positive change in Ankle-Brachial Index) at 30 days, 6 and 12 months
- MAE rate 6 and 12 months post-index procedure
- All-cause death at 30 days, 6 and 12 months
- Clinically-driven TLR and TVR rate at 30 days, 6 and 12 months
- Target limb major amputation at 30 days, 6 and 12 months
- Rate of peri-procedural complications:
 - Perforation at treated segment
 - Abrupt closure at treated segment (including dissection and thrombosis)
 - Significant dissection (types C – F) at treated segment
 - Aneurysm at treated segment
 - Distal embolization

Note that the vessel patency is defined as freedom from more than 50% stenosis based on DUS peak systolic velocity ratio (PSVR) comparing data within the treated segment to the proximal normal arterial segment. A systolic velocity ratio > 2.4 suggests $> 50\%$ stenosis.

No formal tests of hypotheses are proposed for secondary endpoints. Statistical comparisons may be performed for exploratory purposes. No formal inferences are planned on the additional assessments and therefore alpha-adjustments for multiple comparisons will not be used.

All additional assessments are observational.

For Primary endpoint report (30-Day) below Secondary Assessments will be performed:

- Procedural success.
- Clinical success rate at 30 Days.
- Hemodynamic success rate at 30 Days.
- All-cause death at 30 days.
- Clinically-driven TLR and TVR rate at 30 days.
- Clinically-driven TLR and TVR rate at 30 days.

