5.14 Hemodynamic Improvement

The rate of hemodynamic improvement is to assess the changes in ABI from baseline at 1 month, 6 months, and 12 months. The definition of improvement is to observe either the ABI measurement ≥ 0.9 or the change from baseline ≥ 0.1 .

There are two scenarios for hemodynamic improvement shown below.

Subject #1's baseline ABI= 0.95 and 12-month ABI= 1.0. The subject #1 shows 12-month improvement due to 12-month observed ABI= 1.0.

Subject #2's baseline ABI= 0.6 and 12-month ABI= 0.8. The subject is 12-month improvement due to the ABI increase of 0.2 (i.e. 0.8 – 0.6) regardless of 12-month ABI measurement of 0.8 (i.e. <0.1).

Note that the ABI deterioration is defined as observing 0.1 or more in ABI decrease from baseline.

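### Hemodynamic success counts any rise in ABI, so limbs with no true change succeed about half the time by chance, and the thresholded rate in SAP 5.14 does not repair this

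*Protocol*

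**What the plan says.** Protocol 6.2.2 lists "Hemodynamic success rate (defined as positive change in Ankle-Brachial Index) at 30 days, 6 and 12 months". The protocol synopsis, the SAP synopsis and SAP 5.1 carry the same definition, and Table 25.2-1 repeats it: "Hemodynamic success is defined as a positive change in Ankle-Brachial Index compared to baseline". None of these gives a minimum change.

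For the measurement, Table 25.2-1 takes the ankle pressure "at the arteria dorsalis pedis and/or the arteria tibialis posterior" and adds: "If both pressures are measured, the highest pressures will be used for the ABI calculation". It does not ask for the same artery or arteries at each visit.

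A second term, hemodynamic improvement, does have thresholds. Table 25.2-1 defines it as a rise of at least 0.1, or improvement to an ABI of at least 0.90, and requires that no repeat revascularization was needed. SAP 5.14 plans its rate at 1, 6 and 12 months: "The definition of improvement is to observe either the ABI measurement" at or above 0.9, or a change of at least 0.1. SAP 5.14 omits the repeat-revascularization condition. It defines deterioration as a fall of 0.1 or more.

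On status, "there is no control group in this study" (Protocol 7.2.1), and SAP 5.1 states: "No formal tests of hypotheses are proposed for secondary endpoints".

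**The concern.** A responder rate is useful only if a responder is unlikely to arise from measurement error. With the cut at zero, error alone decides the result for any limb that has not changed. In a single-arm study no comparator rate is available to show how much of the reported figure is chance.

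Elsewhere the documents ask for a change of some size before an ABI shift counts:

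- Deterioration in SAP 5.14 needs a fall of 0.1.
- The ABI criterion for clinically driven TLR in Table 25.2-1 is a fall of at least 20% or at least 0.15.
- Pathway PVD (Protocol 4.2.1) required more than 0.1 of "improvement in the ABI during the period from baseline to 30 days post procedure", and no later deterioration above 0.15.

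The listed endpoint is the exception, and it is asymmetric: +0.01 is a success, while −0.09 is not a deterioration.

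At stake is how the 30-day, 6-month and 12-month rates are read. Protocol 4.2.1 quotes 52% hemodynamic success for Pathway PVD. This study would report a figure under the same name but a looser rule, and a result near 50% could look like Pathway's with little or no lasting effect behind it.

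**Working it through.** **Inputs.** The definitions are those above. The documents give no expected rate, power or ABI measurement error for this endpoint, so there is no planned figure to reproduce. The error SDs below are assumptions, shown as a range. Pathway's quoted rates do reproduce: 63/121 = 52.1% and 51/98 = 52.0%.

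**1. Unchanged limb, same artery at both visits.** Let each visit have independent normal error with SD s, so the change has SD s√2.

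- Any rise, continuous values: P(change > 0) = 0.5, whatever s is.
- Any rise, ABI recorded to 0.01 (ties are not successes): P ≈ 1 − Φ(0.005/(s√2)).
- Rise of at least 0.10: P = 1 − Φ(0.10/(s√2)).

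| s (assumed) | s√2 | any rise | any rise, to 0.01 | rise ≥ 0.10 |
|---|---|---|---|---|
| 0.03 | 0.042 | 50% | 45% | 0.9% |
| 0.05 | 0.071 | 50% | 47% | 7.9% |
| 0.07 | 0.099 | 50% | 48% | 15.6% |
| 0.10 | 0.141 | 50% | 49% | 24.0% |

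The chance rate under the plan is about 45% to 50% throughout. Under a 0.10 rule it depends on the error but is at most about a quarter in this range.

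**2. Effect on a reported rate.** Suppose half the limbs truly improve and all of those register a rise, while the rest are unchanged. The plan then reports 0.5 + 0.5 × 0.5 = 75%.

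**3. The improvement rule in SAP 5.14.** Its 0.9 route looks only at the follow-up value.

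- The SAP's own example, baseline 0.95 and 12-month 1.0, is an improvement on a change of 0.05.
- A limb going from 1.00 to 0.90 meets the 0.9 route and, with a fall of 0.10, also meets the SAP's definition of deterioration.

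The documents do not say how many limbs start at or above 0.9, so the size of this cannot be computed.

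**4. Change of arteries between visits, unchanged limb.** The true pressures of the two arteries are taken as equal unless stated.

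- Both arteries at both visits: 47% to 48% (to 0.01). Taking the higher pressure does no harm if it is done consistently.
- Second artery only at follow-up: P(max(X₂, X₃) > X₁) = 2/3 = 66.7% with independent errors. It is 61% with half the error variance shared and 57% with 80% shared. Recorded to 0.01, with none or half shared, it is 59% to 65%.
- Second artery only at baseline: by symmetry 1 − 0.667 = 33% with independent continuous errors. Recorded to 0.01, with none or half shared, it is 31% to 37%.
- Second artery only at follow-up and truly 0.05 to 0.10 higher: 68% to 92%. If truly 0.05 to 0.10 lower: 47% to 59%.

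A 0.10 cut reduces the artery effect but does not remove it. With the second artery only at follow-up and equal pressures, 13.5% to 38.1% of unchanged limbs still pass (s from 0.05 to 0.10, to 0.01).

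**The case against.** The strongest reply is that the SAP already plans a thresholded ABI rate in 5.14, so what remains is which of two rates carries the name success. It is true that a thresholded analysis is planned, and a reader should not infer that none is. But hemodynamic improvement appears in neither the 30-day nor the 12-month report list in SAP 5.1. Its 0.9 route ignores the baseline value, and it drops a condition that the protocol imposes. Nor is 0.1 the smallest change it counts, given that route. It does not stand in for the listed endpoint.

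The second reply is that the stakes are low, and this stands. Protocol 11.3.5 and SAP 5.1 make these assessments observational. Study success rests on 30-day MAE and the acute reduction in stenosis. The documents plan no formal comparison with Pathway PVD, so the 52% matters only as a figure that readers will see beside the new one.

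Third, subjects enter with at least 70% stenosis and Rutherford category 2 to 4, and angioplasty follows atherectomy, so many limbs should truly improve, particularly by 30 days. This also stands. A cohort made up wholly of unchanged limbs is hypothetical. The concern weighs more at 6 and 12 months, when benefit may have been lost.

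Fourth, a reader might infer that the artery rule biases the rate upward. The documents do not support that: they leave the choice of artery open at every visit, and the opposite imbalance lowers the rate.

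**Conclusion.** The point holds as a matter of interpretability, not of study success. Under the listed definition, a limb with no true ABI change is a success about 45% to 50% of the time. The 50% needs only symmetric error. The lower end assumes ABI recorded to 0.01 and a per-visit SD as small as 0.03.

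It is tempting to call this a floor of 50% under the reported rate. It is not one: it applies to unchanged limbs, and limbs that have deteriorated pull the cohort rate lower.

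A change of arteries between visits can move the chance rate up (about 57% to 67% when an artery of equal pressure is added only at follow-up) or down (31% to 37% for the reverse, with ABI to 0.01). The documents do not show which way practice would lean.

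The resulting rate is not like-for-like with Pathway PVD's 52%. SAP 5.14 lessens the problem but does not cure it.

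**What to change.** - In Protocol 6.2.2, Table 25.2-1 and SAP 5.1, with both synopses brought into line, define hemodynamic success as an ABI increase of at least 0.10 from baseline. This is the change criterion already used for hemodynamic improvement. Keep any positive change as a supportive line.
- Report mean ABI change with a 95% CI at 30 days, 6 and 12 months. It needs no threshold.
- In SAP 5.14, apply the ABI ≥ 0.9 route only to limbs with baseline ABI below 0.9, and reconcile the repeat-revascularization condition with Table 25.2-1.
- Where the artery measured is recorded, add a sensitivity analysis that compares the same artery or arteries at both visits. The data collection schedule lists ABI without saying which artery is captured, so this cannot be promised for subjects already measured.

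The cost is wording and one derivation, since ABI is already scheduled at screening and at all three follow-up visits, and the stated success rate will be less favourable. Even then the rate will not match Pathway's exactly, because that study also required no later deterioration above 0.15. Any side-by-side mention should say so.

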### Notes

\*Vessel patency is defined as freedom from more than 50% stenosis based on DUS peak systolic velocity ratio comparing data within the treated segment to the proximal normal arterial segment. A systolic velocity ratio  $> 2.4$  suggests  $> 50\%$  stenosis.

## **7. Study Design**

The JETSTREAM CHINA is a prospective, non-randomized, multicenter, single-arm study to demonstrate the acceptable safety and performance of the JETSTREAM™ Atherectomy System (Jetstream) used during percutaneous peripheral vascular intervention in patients with occlusive atherosclerotic lesions in the native SFA and/or PPA. It is intended that all patients with qualifying lesions would be considered for enrollment and treated with the Jetstream System.

### **7.1. Scale and Duration**

[figure not shown]
The JETSTREAM CHINA trial will be conducted in approximately 10 sites in Mainland China with planned enrollment of approximately 80 subjects, including 20 roll-in subjects with 2 roll-in subjects per site.

The study is planned to have approximately 4 years of enrollment and 1 year of follow up.

All subjects will be screened according to the protocol inclusion and exclusion criteria. Subjects will be enrolled in a non-randomized process. Clinical follow-up will be required at the following time points: pre-discharge, 30 days, 6 and 12 months post-index procedure.

Subjects who are enrolled but the Jetstream System is not used will be followed through the 30-day follow-up visit only.

A schematic of the JETSTREAM CHINA trial design is shown below in Figure 7.1-1.

**Figure 7.1: JETSTREAM CHINA Study Design**

The study will be considered complete after all subjects have completed the 12-month follow-up visit, are withdrawn from the trial (due to death or having been lost to follow-up) or their follow-up window (i.e., 30 days after a scheduled follow-up visit) has closed.

## **7.2. *Treatment Assignment***

Patients who sign the Ethics Committee-approved Informed Consent Form (ICF), and have met all inclusion criteria and none of the exclusion criteria, are eligible to be enrolled in the clinical study. All eligible subjects will receive treatment with the Jetstream System. Enrollment occurs at the time of advancement of the Jetstream catheter into the introducer sheath.

### **7.2.1. *Treatment and Control***

Subjects enrolled in this clinical trial will not be randomized, and there is no control group in this study. All eligible subjects will receive treatment with the Jetstream System.

### **7.2.2. *Target Lesion***

A target lesion is a lesion selected by the Investigator for treatment with the investigational Jetstream System and a study Jetstream catheter. Target lesions must meet all the angiographic selection criteria. A diffuse lesion or multiple lesions (including CTO lesions) within the same target vessel segment can be considered as one target lesion if the total lesion length (including the distance between lesions) is  $\leq 150$  mm.

Only **one** target lesion is allowed in each enrolled subject; and it is decided by physician's discretion in the case that eligible lesions exist in both limbs.

## **7.3. *Multiple Interventions Using Same Access Site during Index Procedure***

### **7.3.1. *Contralateral Limb***

#### **Iliac Lesion**

Using the same access site, iliac lesion(s) in the contralateral limb may be treated during the index procedure under the following conditions:

- Treatment with a commercially available device occurs prior to enrollment of the target SFA/PPA lesion, and
- Treatment of the iliac lesion(s) is deemed an angiographic success without clinical sequelae (success is defined as  $< 30\%$  residual stenosis by visual estimation).

If the above criteria are not met, the subject may not be enrolled to the study but may be rescreened for eligibility after 30 days.

### **7.3.2. Target Limb**

#### **Inflow Lesion**

Using the same access site, additional non-target inflow lesions (including iliac lesion and/or common femoral lesion proximal to the femoral bifurcation) in the target limb may be treated during the index procedure under the following conditions:

- Treatment with a commercially available device occurs prior to enrollment of the target SFA/PPA lesion, and
- Treatment of the inflow lesion(s) is deemed an angiographic success without clinical sequelae (success is measured as < 30% residual stenosis by visual estimation).
- If the above criteria are not met, the subject may not be enrolled to the study but may be rescreened for eligibility after 30 days.

